1.1 Objectives	
Primary Objective:	To determine the efficacy of everolimus in combination with anti-estrogen therapy in patients with ER and/or PR-positive, HER2-negative advanced breast cancer demonstrating disease progression on prior hormonal therapy as measured by PFS
Secondary Objectives:	To determine the safety and tolerability of everolimus with an anti-estrogen therapy in patients with ER and/or PR-positive, HER2-negative advanced breast cancer
Exploratory Objectives:	To evaluate the VeriStrat assay in this HR-positive patient population treated with everolimus in combination with anti-estrogen therapy
1.2 Study Design	
Study Type	 Non-Randomized  Randomized (Allocation Ratio:)
Details	
This is a multi-centered, open-labeled, Phase II study in MBC. The patient population includes locally recurrent or MBC patients with cytologically or histologically confirmed hormone receptor-positive breast cancer who have demonstrated disease progression on prior anti-estrogen therapy or therapies. Eligible patients must have evaluable or measurable disease per RECIST v1.1.
 
Progression Free Survival (PFS), defined as the time from the first day of study drug administration (Day 1) to disease progression (event) as defined by the RECIST v1.1 criteria, or death (event) on study. Patients who are alive and free from disease progression will be censored at the date of last tumor assessment. Patients who receive non-protocol therapy (subsequent therapy) prior to incurring an event will be censored at the date of last tumor assessment prior to the start of subsequent therapy. Patients who do not have a post-baseline tumor assessment will be censored at the date of first treatment (Day 1).
 
Overall Survival (OS), defined as the time from the first day of study drug administration (Day 1) or death on study. Patients who are alive will be censored at the date of last known date alive.
 
Duration of Response (DOR), is defined as the time from the first date of CR or PR to disease progression or death as defined by the RECIST v1.1 criteria. Patients who are alive and free from disease progression will be censored at the date of last tumor assessment. Patients who receive non-protocol therapy (subsequent therapy) prior to incurring an event will be censored at the date of last tumor assessment prior to the start of subsequent therapy. Only those patients who achieved CR or PR will be included in the summaries of DOR.
 
PFS (efficacy primary endpoint), OS and DOR (efficacy secondary endpoints) estimates will be generated using Kaplan-Meier methods, both for all patients enrolled and those patients receiving the MTD. Four month and six month PFS estimates with 95% confidence intervals (CIs), and median PFS and OS with 95% CIs, will be calculated.
 
Best overall response will be tabulated: CR, PR, SD, PD and not evaluable (NE).
 
Overall Response Rate (ORR) is defined as the proportion of patients with observed complete response (CR) or partial response (PR) according to the RECIST v1.1 criteria.
 
Clinical Benefit Rate (CBR) is defined as the proportion of patients with CR, PR or SD x 6 months according to the RECIST v1.1 criteria.
 
For ORR and CBR, patients without a post-baseline tumor assessment will be classed as not evaluable (NE) and considered as non-responder.


	For ORR and CBR, the estimates and the associated 95% CI (based on both asymptotic normal approximation and exact binomial methods) will be calculated.
1.3.2 Randomization	
Randomization Type:	 Open-Label  Single Blind  Double-Blind
1.4 Timing of Analysis	
Planned Interim Analysis	 Cohort Review / Dose Escalation  Safety Review  Interim Efficacy/Safety Analysis  Independent DMC/DSMB  Annual Report / Investigator Brochure (IB)  Abstract / Scientific Presentation (Oral/Poster)
Final Analysis	The final analysis will occur when 42 patients have discontinued treatment, progressed, died or are still on treatment but have at least 12 months of follow-up (time from first treatment until last tumor assessment).
1.5 Responsibilities	
Trial Statistician:	Prepare SAP check list and TFL shells Review deliverables produced by Statistical Programmer
PK Statistician:	N/A
Independent Statistician:	N/A
1.6 Analysis Software	
Main statistical analysis:	SAS Version 9.3 or above
Other analysis software:	N/A
1.7 Coding	
 Adverse Events  Medical History	 MedDRA:  Version  Most current release and update coding with new major releases  NCI-CTCAE Version 4.03
 Concomitant Medication  Prior Therapy  Subsequent/Further Therapy	 WHO-Drug:  Version  Most current release and update coding with new major releases

2 Analysis Population	
Intent-To-Treat (ITT) Population definition:	 All patients who have started treatment in the study  All patients who have been randomized in the study, regardless of whether they have received any treatment or not  All patients who have been randomized and have started treatment in the study  Other definition, specify:
Per Protocol (PP) Population to be used in analysis:	 Yes  No If yes, please specify the criteria for exclusion from the PP population:
Safety (SAF) Population definition	 All patients who have started treatment in the study. Patients will be analyzed according to the actual treatment they have received.  Other definition, specify: All patients who have received any dose of study treatment.
Other Analysis Population definition:	Efficacy Evaluable (EE): All patients who receive at least 1 cycle of study treatment and have at least one post-baseline assessment. (Patients who discontinue treatment during Cycle 1 will not be replaced in the study.)
3 Baseline Value Definitions	
	Last value prior to first date of study treatment
4 Efficacy	
Response Criteria Used:	 RECIST 1.0  RECIST 1.1  Cheson 2007  Modified RECIST – specify:  Other criteria, Specify:
Efficacy Assessment Timepoints:	
Response Assessment Every 2 Cycles Patients will be reevaluated for response to treatment after every 2 cycles of treatment, prior to the start of odd-numbered cycles.
 
End of Study Treatment. The follow-up evaluations required after treatment ends (due to disease progression, or once the patient is discontinued due to unacceptable toxicity or decision to discontinue treatment by the patient or the study physician) are specified in Appendix D.
 
Follow-up for Patients Who Discontinue Prior to Disease Progression Patients who discontinue study treatment prior to the occurrence of disease progression will be followed every 3 months (\pm 1 month) from the date of last dose of study drug until disease progression or for up to 3 years from the start of treatment whichever comes first. Assessments at these visits will be performed as described in Appendix D.
 
Survival Follow-up After disease progression is documented, patients will be followed every 3 months (\pm 1 month) for survival (e.g., date and cause of death) for up to 3 years from the start of treatment or death whichever comes first.

Efficacy Endpoints:		
  
 	Endpoint	Primary Analysis Population	Other Analysis Population	
   
 Primary	PFS	Efficacy Evaluable	Safety	
 
 Secondary	OS, DOR, ORR, CBR	Efficacy Evaluable	Safety	
  
					Endpoint	Primary Analysis Population	Other Analysis Population	Primary	PFS	Efficacy Evaluable	Safety	Secondary	OS, DOR, ORR, CBR	Efficacy Evaluable	Safety											
	Endpoint	Primary Analysis Population	Other Analysis Population																									
Primary	PFS	Efficacy Evaluable	Safety																									
Secondary	OS, DOR, ORR, CBR	Efficacy Evaluable	Safety																									
Definition of Terms:																												
 Response	 Complete Response + Partial Response as best observed response  Complete Response + Partial Response, confirmed with weeks apart.  Other criteria, specify:																											
 Clinical Benefit	 Complete Response + Partial Response + Stable Disease as best observed response  Complete Response + Partial Response (confirmed with weeks apart) + Stable Disease (at least weeks from start of treatment)  Other criteria, specify: (Complete response (CR) + Partial response (PR) + Stable disease (SD) x 6 months)																											
 Progression	Disease progression (event) as defined by the RECIST v1.1 or death on study; non-protocol therapy (subsequent therapy) prior to incurring an event will be censored at the date of last tumor assessment prior to the start of subsequent therapy																											
 Subsequent Therapy	Non-protocol therapy prior to incurring an event																											
 Treatment Failure	N/A																											
Definition of Endpoints:	Start Date:  Date of Randomization  Date of First Treatment End Date (specify for all pertinent endpoints): Overall Survival: Event = Death 
  
 Situation	Date of Event or Censoring	Outcome	
   
 Death, while on-study or follow-up	Date of death	Event	
 
 Alive, as of end of study or follow-up	Date last known alive	Censored	
 
 Status unknown, as of end of study	Date last known alive	Censored	
  
 Progression-Free Survival: Event = Progression or Death 
  
 Situation	Date of Event or Censoring	Outcome	
   
 No baseline assessment	Date of first treatment	Censored	
 
 PD documented between scheduled visits, did not die, and received no subsequent therapy	First date of evaluated overall response = PD	Event	
 
 PD documented between scheduled visits, did not die, but received subsequent therapy prior to incurring progression event	Date of last evaluable tumor assessment prior to start of subsequent therapy	Censored	
  
				Situation	Date of Event or Censoring	Outcome	Death, while on-study or follow-up	Date of death	Event	Alive, as of end of study or follow-up	Date last known alive	Censored	Status unknown, as of end of study	Date last known alive	Censored	Situation	Date of Event or Censoring	Outcome	No baseline assessment	Date of first treatment	Censored	PD documented between scheduled visits, did not die, and received no subsequent therapy	First date of evaluated overall response = PD	Event	PD documented between scheduled visits, did not die, but received subsequent therapy prior to incurring progression event	Date of last evaluable tumor assessment prior to start of subsequent therapy	Censored
Situation	Date of Event or Censoring	Outcome																										
Death, while on-study or follow-up	Date of death	Event																										
Alive, as of end of study or follow-up	Date last known alive	Censored																										
Status unknown, as of end of study	Date last known alive	Censored																										
Situation	Date of Event or Censoring	Outcome																										
No baseline assessment	Date of first treatment	Censored																										
PD documented between scheduled visits, did not die, and received no subsequent therapy	First date of evaluated overall response = PD	Event																										
PD documented between scheduled visits, did not die, but received subsequent therapy prior to incurring progression event	Date of last evaluable tumor assessment prior to start of subsequent therapy	Censored																										

	Death while on-study without previous PD, and received no subsequent therapy	Date of death	Event		
	Death while on-study and had previous PD, and received no subsequent therapy	First date of evaluated overall response = PD	Event		
	Death while on-study without previous PD, but received subsequent therapy prior to death event	Date of last evaluable tumor assessment prior to start of subsequent therapy	Censored		
	Death while on-study and had previous PD, but received subsequent therapy prior to PD event	Date of last evaluable tumor assessment prior to start of subsequent therapy	Censored		
	No progression, no death	Date of last evaluable tumor assessment	Censored		
	Treatment discontinuation for adverse event or other non-event reason	Date of last evaluable tumor assessment	Censored		
 Overall Response Rate (ORR)	Default: Estimates of rates in each treatment arm				
 Disease Control Rate (DCR)	 Difference in rates & 95% confidence interval between treatment arms  p-value, specify statistical test:				
 Clinical Benefit Rate (CBR)					
 Early Progression Rate (EPR)					
 Time To Progression (TTP)	Default: Estimates of medians in each treatment arm				
 Progression-Free Survival (PFS)	 Other quartiles or percentages of survival required, specify: PFS: @4 months and 6 months: percentages & 95% confidence intervals  Hazard ratio & 95% confidence interval between treatment arms, unstratified  p-value, specify statistical test:				
 Overall Survival (OS)					
 Duration of Response	 Hazard ratio & 95% confidence interval between treatment arms, stratified (specify stratification factor(s)):  p-value, specify statistical test:				
 Duration of Stable Disease					
 Time To Treatment Failure (TTF)					
 Other, Specify:	Median Follow-up: Estimate of median, 25 th and 7 th quartiles; Follow-up point estimates: @ 4 months, 6 months, and 12 months: percentages & 95% confidence intervals				
5 Safety					
Adverse Events	Definition of Treatment-Emergent Adverse Event (TEAE): Treatment-emergent AEs are those with an onset on or after the initiation of therapy				
Laboratory Data	Data will be summarized by:  NCI-CTCAE for CTCAE-gradable parameters, and H/L for non-CTCAE-Gradable parameter  H/L for all lab parameters				

Tier 1 Study – Tables, Figures & Listings

Standard TFLs			
Table No	Description	Variables/Analyses To Be Included	Population
Table 1	Patient Disposition	 Number of patients screened  Number of patients enrolled  Number of patients treated  Reason for treatment discontinuation  Reason for study discontinuation  Other, specify:	Enrolled Patients
Table 2	Demographic Characteristics	 Age: N, Mean, SD, Median, Min, Max  Age Group: <65, >=65  Sex  Race  Ethnicity  ECOG  Other, specify:	Enrolled Patients
Table 3	Disease History - General	 Histology  Disease staging at initial diagnosis  Time from initial diagnosis to first dose  Number of patients with metastatic disease  Sites of metastases  Other, specify: Histology Grade	Enrolled Patients
Table 4	Prior Hormonal Therapy	Time [months] from last hormonal therapy to first date of study treatment: N, Mean, SD, Median, Min, Max	Safety
Table 5	Treatment and Dose Modifications	Duration on Treatment (weeks), N, Mean, SD, Median, Min, Max Dose Reduction (n, %) None Patients with 1 Patients with 2 Patients with >= 3 Dose Interruption (n, %) None Patients with 1 Patients with 2 Patients with >= 3	Safety
Table 6	Measurable Lesions	Measurable Lesions (n, %) Non-Measurable Lesions (n, %) Evaluable Bone Only Disease (n, %)	Enrolled Patients
Table 7	Best Overall Response	Best overall response (n, %): Complete response (CR), Partial response (PR), Stable disease (SD), NonCR/NonPD, Progressive disease (PD), Not evaluable (NE), Not applicable (N/A) Missing Objective Response Rate (ORR) (= CR+PR): ORR, 95% Confidence interval Clopper-Pearson	Efficacy Evaluable, Safety

Standard TFLs			
Table No	Description	Variables/Analyses To Be Included	Population
		Normal Approximation Clinical Benefit Rate (CBR) $(=CR+PR+SD \geq 4 \text{ months})$: CBR, 95% Confidence interval Clopper-Pearson Normal Approximation Clinical Benefit Rate (CBR) $(=CR+PR+SD \geq 6 \text{ months})$: CBR, 95% Confidence interval Clopper-Pearson Normal Approximation]	
Table 8	Progression-free Survival (Kaplan-Meier estimates & 95% CI)	Number of patients with events, Number of patients censored, Median Progression-free Survival [months (95% CI)] 25% Percentile Follow-up [months (95% CI)] 75% Percentile Follow-up [months (95% CI)] Progression-free Survival Estimates [probability, (95% CI)]: 4 months, 6 months, 12 months	Efficacy Evaluable, Safety
Table 9	Overall Survival (Kaplan-Meier estimates & 95% CI)	Number of patients with events, Number of patients censored, Median Overall Survival [months (95% CI)] 25% Percentile Follow-up [months (95% CI)] 75% Percentile Follow-up [months (95% CI)] Overall Survival Estimates [probability, (95% CI)]: 4 months, 6 months, 12 months	Efficacy Evaluable, Safety
Table 10	Adverse Event Overview	Any Adverse Event Treatment-related Adverse Event Everolimus-related Adverse Event Anti-Estrogen Therapy-related Adverse Event Serious Adverse Event Treatment-related Serious Adverse Event Serious Adverse Event leading to Death Treatment-related Serious Adverse Event leading to Death Adverse Events leading to Treatment Discontinuation Adverse Events leading to Treatment Interruption Adverse Events leading to Treatment Reduced	Safety

Standard TFLs			
Table No	Description	Variables/Analyses To Be Included	Population
Table 11	Any Treatment-Emergent Adverse Event by System Organ Class and Preferred Term	System organ class, Preferred term, CTCAE grade [all statistics: (n, %)]	Safety
Table 12	Any Treatment Related-Emergent Adverse Event by System Organ Class and Preferred Term	System organ class, Preferred term, CTCAE grade [all statistics: (n, %)]	Safety
Table 13	Any Treatment Related-Emergent Adverse Event by SCRI Grouped Adverse Event Term	SCRI grouped AE term, CTCAE grade [all statistics: (n, %)]	Safety
Table 14	Treatment Serious-Emergent Adverse Event by System Organ Class and Preferred Term	System organ class, Preferred term, CTCAE grade [all statistics: (n, %)]	Safety
Table 15	Treatment Related and Serious-Emergent Adverse Event by System Organ Class and Preferred Term	System organ class, Preferred term, CTCAE grade [all statistics: (n, %)]	Safety
Table 16	Duration of Response (DOR) (Kaplan-Meier estimates & 95% CI)	Number of patients with events, Number of patients censored, Duration of Response: Median [months (95% CI)] Duration of Response Estimates [probability, (95% CI)]: 4 months, 6 months	Efficacy Evaluable, Safety
Table 17	Median Follow-up (Kaplan-Meier estimates & 95% CI)	Number of patients with events, Number of patients censored, Median Follow-up [months (95% CI)] 25% Percentile Follow-up [months (95% CI)] 75% Percentile Follow-up [months (95% CI)] Follow-up Estimates [probability, (95% CI)]: 4 months, 6 months, 12 months	Efficacy Evaluable
Table 18	Genetic Abnormalities	Patients with: Any abnormality (n, %) Abnormality in PI3K/Akt/mTOR pathway (n, %) ESR1 abnormality (n, %)	Safety

Figure No	Description	Variables/Analyses To Be Included	Population
Figure 1	Overall Survival	Timescale to be used on horizontal axis:  Day  Week  Month  Year	Efficacy Evaluable, Safety
Figure 2	Progression-free Survival	Timescale to be used on horizontal axis:  Day  Week  Month  Year	Efficacy Evaluable, Safety

Listing No.	Title	Variables/Analyses To Be Included	Population
1	Prior Systemic Therapy	Patient Number Start Date End Date Medication Taken Regimen Number Disease Setting Best Overall Response Reason Therapy Ended - Specify	Enrolled Patients
2	Current Hormonal Therapy	Patient Number Visit Name Disease Setting Medication Taken Start Date End Date Reason for Therapy End	Enrolled Patients
3	Biodesix Information	Patient Number Age Sex Race Ethnicity Performance Status at Screening (ECOG) ER (most recent) PR HER 2 Current Endocrine Therapies Prior Endocrine Therapies Prior Adjuvant Therapies Prior Metastatic Therapies Prior Neoadjuvant Therapies Disease Stage at Diagnosis Date of Treatment Start Best Overall Response Date of Best Overall Response PFS (months) OS (months)	Enrolled Patients
4	Patients with ESR1 Mutation	Patient Number	Safety, whose Tissue Samples were Assessed

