10.4.2 Efficacy Analysis

All efficacy analyses will be performed using the Efficacy Evaluable Population.

- Overall Response Rate (ORR) is defined as the proportion of patients with observed complete response (CR) or partial response (PR) according to the RECIST v1.1 criteria.
- Clinical Benefit Rate (CBR) is defined as the proportion of patients with CR, PR or SD x 6 months according to the RECIST v1.1 criteria.
 - For ORR and CBR, patients without a post-baseline tumor assessment will be classed as not evaluable (NE) and considered as non-responder.
- Progression Free Survival (PFS), defined as the time from the first day of study drug administration (Day 1) to disease progression (event) as defined by the RECIST v1.1 criteria, or death (event) on study. Patients who are alive and free from disease progression will be censored at the date of last tumor assessment. Patients who receive non-protocol therapy (subsequent therapy) prior to incurring an event will be censored at the date of last tumor assessment prior to the start of subsequent therapy. Patients who do not have a post-baseline tumor assessment will be censored at the date of first treatment (Day 1).
- Overall Survival (OS), defined as the time from the first day of study drug administration (Day 1) or death on study. Patients who are alive will be censored at the date of last known date alive.
- Duration of Response (DOR), is defined as the time from the first date of CR or PR to disease progression or death as defined by the RECIST v1.1 criteria. Patients who are alive and free from disease progression will be censored at the date of last tumor

CONFIDENTIAL

STUDY DRUG(S): EVEROLIMUS
FINAL PROTOCOL DATE: 19 JUNE 2014

SCRI INNOVATIONS STUDY NUMBER: BRE 212
VERSION 1.0

assessment. Patients who receive non-protocol therapy (subsequent therapy) prior to incurring an event will be censored at the date of last tumor assessment prior to the start of subsequent therapy. Only those patients who achieved CR or PR will be included in the summaries of DOR.

- Percentage of patients progression-free at 4 and 6 months, defined as the proportion of patients who are progression-free as defined by the RECIST v1.1 starting from the date of their first treatment.

For ORR and CBR, the estimates and the associated 95% CI (based on both asymptotic normal approximation and exact binomial methods) will be calculated.

Best overall response will be tabulated: CR, PR, SD, PD and not evaluable (NE).

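### The SAP's PFS table censors for treatment discontinuation, a rule absent from Protocol 10.4.2 and SAP 1.2, with no stated precedence over later progression and no limit on the censoring date

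*SAP*

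**What the plan says.** Protocol 10.4.2 and SAP 1.2 define PFS as the time from first dose to RECIST 1.1 progression or death on study. Neither makes the event depend on whether the patient is still on treatment. Both give the same three censoring rules:

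- "Patients who are alive and free from disease progression will be censored at the date of last tumor assessment".
- Patients who start non-protocol therapy before an event are censored at the last assessment before that therapy.
- Patients with no post-baseline tumor assessment are censored on Day 1.

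The PFS table in SAP section 4 (Efficacy, Definition of Endpoints) adds "Treatment discontinuation for adverse event or other non-event reason", censored at the last evaluable tumor assessment. Other rows of that table bear on it:

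- "No progression, no death" has the same date and the same outcome.
- "PD documented between scheduled visits, did not die, and received no subsequent therapy" is an event. It is the only progression event row for a patient who has not died.
- "Death while on-study without previous PD, and received no subsequent therapy" is an event.
- The subsequent-therapy rows limit their date: "Date of last evaluable tumor assessment prior to start of subsequent therapy".

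The OS table uses a wider phrase for its event: "Death, while on-study or follow-up".

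Protocol 7.6.1 and the SAP's Efficacy Assessment Timepoints both follow patients who stop before progression every 3 months (± 1 month), until progression or 3 years from the start of treatment. Protocol Appendix D schedules CT at those visits.

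**The concern.** Take a patient who stops for toxicity, takes no new therapy and progresses at a 3-month follow-up scan. Protocol 10.4.2 and SAP 1.2 count an event. The discontinuation row also fits this patient and says censored. The phrase about a non-event reason describes why treatment stopped, not what happened afterwards, so it does not settle the matter, and no precedence is given. The same collision arises for a death after stopping if on-study in the PFS rows includes off-treatment follow-up. The wider OS wording leaves that unclear.

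The date is a second problem. It is not limited to assessments before stopping or before new therapy. For a patient who stops and then progresses, the last evaluable assessment can be the progression scan itself. For a patient who starts new therapy, it can differ from the date that the subsequent-therapy rows give.

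This is the primary endpoint of a single-arm study planned around a median of 2.8 versus 5 months. No comparator arm shares the censoring rule, so any distortion enters that comparison directly.

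**Working it through.** **What the plan supplies.** Protocol 10.2 gives 42 evaluable patients, 18 months of accrual, 12 months of further follow-up, and medians of 2.8 and 5 months. The plan gives no figure for stopping before progression. Its sample size does not depend on this row, and it reproduces closely: with S₀ = 0.500 and S₁ = 0.5^(2.8/5) = 0.678 at 2.8 months, (1.645 + 0.842)² × 0.678 × 0.322 / 0.178² ≈ 42.4, against the stated 42. The calculator's formula is not in the documents; this variant uses the variance under the alternative.

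**Assumptions not in the documents.** Exponential PFS with hazard λ = ln 2 / median. A share p = 10%, 20% or 30% stops before progression, with stopping hazard μ = λp/(1 − p). The hazard is unchanged after stopping unless stated. A share q of those who stop starts new therapy at once and is censored under either rule. Administrative censoring is uniform on 12 to 30 months.

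**Events.** Under the protocol rule:

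42 × [1 − (e^(−12λ) − e^(−30λ)) / (18λ)]

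For a median of 5.0, λ = 0.1386, giving 42 × [1 − (0.1895 − 0.0156)/2.495] = 39.1. If the row overrides later progression, λ is replaced by λ/(1 − p) and the result is multiplied by (1 − p). At p = 20%: 42 × 0.8 × [1 − (0.1250 − 0.0055)/3.119] = 32.3, a loss of 6.8. The loss scales with (1 − q).

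| | p = 10% | p = 20% | p = 30% |
|---|---|---|---|
| Median 5.0, lost of 39.1, q = 0 | 3.3 | 6.8 | 10.4 |
| Median 5.0, q = 50% | 1.6 | 3.4 | 5.2 |
| Median 5.0, q = 80% | 0.7 | 1.4 | 2.1 |
| Median 2.8, lost of 41.5, q = 0 | 4.0 | 8.1 | 12.2 |

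**Median if censored at stopping.** With an unchanged hazard, Kaplan-Meier still returns 5.00. At p = 20%, holding the protocol-rule median at 5.0, the shift is −2.2% if the post-stop hazard is multiplied by 0.75 and +6.4% if it is doubled.

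**Median if censored at the progression date.** With q = 0, the hazard that Kaplan-Meier estimates is λe^(−μu), because stopped patients stay in the risk set but their events are removed. The median solves ((1 − p)/p)(1 − e^(−μt)) = ln 2. At p = 20%, μ = 0.0347, so 1 − e^(−μt) = 0.1733 and t = 5.49. The 6-month rate is exp[−4(1 − e^(−0.2079))] = 47.2%.

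| Progression-date reading, true median 5.0 | p = 10% | p = 20% | p = 30% |
|---|---|---|---|
| Median, q = 0 (months) | 5.20 | 5.49 | 5.93 |
| Median, q = 50% (months) | 5.10 | 5.24 | 5.44 |
| 6-month PFS, q = 0 (true 43.5%) | 45.2% | 47.2% | 49.7% |

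**With scheduled scans.** Simulation of 2,000 trials per setting used 56-day scans on treatment, 3-month scans after stopping, q = 0 and an unchanged hazard. Three scan intervals are 168 days, or 5.52 months. The typical reported median was 5.52 months at every p, both under the protocol rule and when censoring at the last scan before stopping. When censoring at the progression scan, the mean of the trial medians rose from 5.92/5.92/6.05 to 6.14/6.50/7.20 months at p = 10%/20%/30%. That median exceeded the protocol-rule median in 15%/35%/57% of trials and was never lower.

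**The case against.** The best defense is that one reading fits every passage. The PFS table counts progression or death as the event, and SAP 1.2, the SAP's definition of progression and Protocol 10.4.2 attach no treatment condition. On that view the row means only patients who stopped and never had an event, and it merely repeats the row above it. Read with equal literalness, the table has no event row for a living patient whose progression is found at a scheduled scan, and no programmer would apply that. For patients who start new therapy, the general rule already limits the date.

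That reading is available, but the SAP does not state it. If it is what the sponsor intends, the row does nothing and can be deleted or restricted. The missing event row for scheduled scans also leaves the table without an explicit entry to outrank the discontinuation row.

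Three objections on size stand. The shifts in the median on the progression-date reading require a programmer to recognize a progression scan and still use it as a censoring date, so they are not the expected impact. Censoring at the last scan before stopping loses events but left the typical reported median unchanged in the simulation. Every event loss rests on assumed stopping and new-therapy rates and is small if most stoppers start new therapy. In addition, Protocol section 6 keeps patients who stop everolimus on anti-estrogen therapy if they are benefiting, so some may not count as having stopped treatment.

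**Conclusion.** The concern holds and should be fixed. The SAP table states a censoring rule that is either redundant or contrary to the primary endpoint definition in Protocol 10.4.2 and SAP 1.2, and nothing in the SAP says which. This follows from the text alone.

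The size depends on assumptions. Under the override reading, at a true median of 5 months, the loss ranges from 0.7 of 39.1 events (10% stop, 80% of them start new therapy at once) to 10.4 (30% stop, none do). The Kaplan-Meier median is biased upward even with an unchanged hazard only if the progression scan is used as the censoring date. If patients are censored at stopping, bias depends on whether stopping is informative. I claim no general shift in the median, and no general widening of its confidence interval, when censoring is at the last scan before stopping.

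**What to change.** Delete the row from the primary PFS table, or restrict it to patients with no later progression or death. State the precedence:

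1. The first RECIST progression, at a scheduled or unscheduled assessment, or death, if it occurs before subsequent therapy, is an event, including after treatment discontinuation.
2. If subsequent therapy comes first, censor at the last evaluable assessment before it.
3. Otherwise censor as in Protocol 10.4.2 and SAP 1.2.

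If discontinuation censoring is wanted, make it a labelled sensitivity analysis dated at the last evaluable assessment before stopping. Name the drug or drugs whose discontinuation counts: Protocol 11.1.5 uses study treatment to mean everolimus for adverse event reporting, while section 6 provides for anti-estrogen therapy to continue after everolimus stops in patients who benefit.

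In the same edit, reconcile on-study in the PFS rows with the wider phrase in the OS row. Add the Day 1 row for patients with no post-baseline tumor assessment, and leave the row for no baseline assessment in place. The Day 1 row matters mainly for the Safety-population analysis, since the Efficacy Evaluable set already requires a post-baseline assessment.

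The cost is SAP wording and programming. No new data are needed, because off-treatment scans and survival follow-up are already planned. The one drawback is that progression after stopping is dated on 3-month (± 1 month) scans instead of 8-week scans, so some dates will be less precise.
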